Randomization. We will randomize each cohort of six to either WCBT or VAU, until 17 WCBT and 17 VAU groupings are completed at JVSLA and 8 WCBT and 8 VAU groupings are completed at JVSD. In our R34, there was a median wait time of 15 days from assessment to randomization and median wait times were identical for WCBT (2.14 weeks) and VAU (2.14 weeks). We will not reduce group size in response to a longer-than-expected wait. We will re-assess participants on key assessment measures immediately prior to randomization for those who wait beyond one week. In our R34, groups assembled every two to three weeks and the randomization scheme was acceptable (100% of qualified participants agreed to be randomized). Participants will receive \$20 for attending randomization meeting. This reimbursement is for travel and any meals missed during the meeting.

Selection and delivery of the control condition. The proposed study aims to test the effect of WCBT on social anxiety and employment outcomes among unemployed, job seekers with SocAD. A comparison to treatment as usual is considered to be the most appropriate comparison condition for an effectiveness study because evidence-based psychosocial treatments for social anxiety are currently not provided for most unemployed people with social anxiety disorder. Thus, comparison to vocational services as usual (VAU) best tests an effectiveness-based hypothesis that WCBT leads to improved outcomes for work-seeking persons with social anxiety as compared to services as usually delivered in a vocational rehabilitation setting.

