We will use the same MLM approach that we used in our R34 pilot to compare individuals assigned to WCBT vs. VAU. 3-level models will incorporate repeated measures on individuals nested within the 50 6-person groups randomly assigned to WCBT or VAU. HLM software will be used (115). Individual baseline scores on each outcome variable will be incorporated as level 2 covariates to increase the precision and statistical power of tests of the randomized intervention and reduce regression to the mean artifacts (116). Observations will be centered at a post-intervention or follow-up time point to provide a straightforward WCBT vs. VAU comparison on outcome level. Persistence of intervention effects will be assessed through WCBT vs. VAU comparisons on the level 2 slopes characterizing individual outcome trajectories through 52-week follow-up; quadratic or piecewise slope terms (117) will be included if needed to reflect acceleration or slowing of change over time. Power estimates for the planned MLM analyses were conducted using Optimal Design software (118). The entire sample of 300 individuals, nested within 50 groups, with 5 assessments over time, will provide power of .8 to detect (at 2-tailed $p < .05$) an intervention effect on intercept or slope of at least $d=0.34$; power estimates range from .7 to detect $d=.30$ to .9 to detect $d=.39$. Effect sizes in the R34 pilot ranged from .46 for hours worked to 1.36 for social avoidance; this suggests that power in this larger R01 will be adequate to detect condition differences on all outcomes, including employment. These estimates assume a minimum intraclass correlation (ICC) between groups of .01, which is larger than the ICCs observed in the R34 pilot. If the ICC for the R01 is found to be substantially higher at .03, the effect size detectable with power of .8 will rise only slightly, from $d= .34$ to $d=.36$.

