General approach to quantitative analysis. All raw data will be examined to verify quality and identify potential outliers and distributional issues that may require transformation or nonlinear link functions, including survival functions for variables subject to censoring (e.g., time to job loss). Psychometric properties of all measures will be verified in the study sample. Adequacy of randomization will be verified through multivariate comparisons of intervention and control arms on all baseline variables, using 2-level mixed effects regression models (individuals nested in groups). Variables showing significant baseline differences will be considered as covariates in subsequent analyses. Primary analyses will involve the ITT sample of all individuals who completed the baseline interview and were randomized. If there is sufficient variability in fidelity, participation, or drop-out, parallel secondary outcome analyses will incorporate measures of intervention dosage (i.e., attendance and participation) and fidelity as covariates, to account for variation in intervention engagement and retention. Additional analyses will identify characteristics of individuals who drop out or receive lower dosage. Covariates of treatment drop-out will be used to estimate complier average causal effects (126). Assessment attrition will be minimized through use of incentives and proactive retention strategies. In our pilot, our post-intervention retention rate was 86%; retention was equal across arms; no baseline variables were found to be related to attrition; and missing data patterns were not related to study outcomes. As in the pilot study, we will use pattern mixture modeling (127) to determine whether missing assessments at various time points affect study conclusions or are “ignorable” (i.e., conditionally missing at random). Missing data determined to be ignorable will be estimated using expectation maximization and multiple imputation procedures appropriate for longitudinal data (128). Sensitivity analysis will be used to examine the possible impact on study conclusions involving any missing data found to be nonignorable (129).

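### Beyond the prespecified baseline outcome score, covariates are considered from significance tests of baseline imbalance, which leaves paid work hours with no useful fixed adjustment

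*Combined protocol and SAP*

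**What the plan says.** Two parts of the section on power analysis and statistical strategy deal with covariates.

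- **Aim 1** fixes one covariate in advance for every outcome: "Individual baseline scores on each outcome variable will be incorporated as level 2 covariates to increase the precision and statistical power of tests". This applies whatever the observed balance, and its stated purpose is precision.
- **General approach to quantitative analysis** governs anything further. "Adequacy of randomization will be verified through multivariate comparisons of intervention and control arms on all baseline variables", using two-level mixed models, and then "Variables showing significant baseline differences will be considered as covariates in subsequent analyses". No list or number of variables is given, no significance threshold, and no rule for moving from considering a variable to entering it. The step is not confined to sensitivity analyses.

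The Randomization section allocates whole cohorts of six "until 17 WCBT and 17 VAU groupings are completed at JVSLA and 8 WCBT and 8 VAU groupings are completed at JVSD". Site is therefore balanced between arms by construction. Site appears under Aim 3 as a moderator, but the Aim 1 text does not name it as a covariate.

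Under Measures of employment, the primary work-related outcome is weekly paid work hours during follow-up. The inclusion criteria require participants to be unemployed. In Table 4 the employment follow-up questionnaire starts at 12 weeks and the MSIF work-performance rating at post-treatment.

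**The concern.** When cohorts are properly randomised, a significant baseline difference is a chance event. It carries no information on whether the variable predicts the outcome. A rule based on significance can bring in an irrelevant scale that happens to differ between arms, and leave out a strong predictor that happens not to.

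Three things are at stake:

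- **Precision.** Adjustment reduces variance when the covariate predicts the outcome and is always in the model. At a .05 threshold, a given covariate qualifies in only about one trial in twenty.
- **Prespecification.** The additional covariates in the main comparisons are unknown until the arms have been compared, and the choice is then left to the analyst.
- **Site.** The two agencies differ markedly; the Study Sites section gives 40% with bachelor's degrees in Los Angeles and 5% in Detroit. Because the arms are balanced on site, an imbalance test would not be expected to select it.

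For work hours the rule carries more weight than elsewhere, because the one covariate fixed in advance has almost no spread.

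**Working it through.** **Inputs from the plan (Aim 1).** "The entire sample of 300 individuals, nested within 50 groups, with 5 assessments over time"; two-sided .05; power .80 at d = .34. "These estimates assume a minimum intraclass correlation (ICC) between groups of .01".

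**Step 1. Reproduce the stated power, with no covariate.** For 50 group means of 6 people and unit outcome variance:

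SE = √[4 × (ICC + (1 − ICC)/6) / 50] = √[4 × (.01 + .165) / 50] = √.0140 = .1183.

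With 48 df and non-centrality .34/.1183 = 2.87, power is .804. The same formula gives .700 at d = .30, .898 at d = .39, and .813 at d = .36 with ICC .03. All agree with the plan, so the stated power does not rely on covariates.

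**Step 2. How often would the rule be triggered?** Table 4 lists 21 instruments with a baseline assessment. If each gave one independent test at .05 (an assumption, since the plan gives neither number):

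- expected chance findings = 21 × .05 = 1.05;
- P(at least one) = 1 − .95^21 = .66.

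For 10 to 40 variables the range is .40 to .87. The instruments overlap, which lowers the figure: for 21 tests with a common correlation of .3 or .5 (assumed), simulation gives .55 or .43.

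**Step 3. An outcome without a useful baseline score (paid work hours).** Take one baseline covariate with correlation r with the outcome. The values of r are assumptions; the plan gives none. If the covariate is always in the model:

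SE² = .0140 × (1 − r²) × 47/46, with 47 df.

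- r = .4: SE = .1096, non-centrality .34/.1096 = 3.10, power .86.
- r = .6: SE = .0957, non-centrality .34/.0957 = 3.55, power .94.

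For the rule, trials were simulated on 50 group means, entering the covariate only when its arm test gave p < .05 (100,000 runs per setting):

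| r | No covariate | Rule | Prespecified | Type I error under rule |
|---|---|---|---|---|
| .3 | .80 | .80 | .83 | .048 |
| .4 | .80 | .81 | .86 | .047 |
| .5 | .80 | .81 | .89 | .043 |
| .6 | .81 | .82 | .94 | .041 |

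At r = .5 the variance of the effect estimate is .0140 unadjusted, .0131 under the rule and .0107 prespecified. The rule keeps (.0140 − .0131)/(.0140 − .0107), about 27% of the available gain.

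**Step 4. An outcome with an informative baseline score.** Put the baseline score in the model (assumed r = .5 with the outcome) and add one further covariate at r = .4:

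| Correlation between the two covariates | Baseline score only | Rule added | Both prespecified |
|---|---|---|---|
| 0 | .90 | .90 | .95 |
| .2 | .90 | .90 | .92 |
| .4 | .89 | .89 | .91 |

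Most of the benefit comes from the baseline score that the plan already fixes. Type I error under the rule is .045 to .048 here.

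**The case against.** The best reply is that the plan already prespecifies the most important covariate. That stands. A reader might infer from the general section alone that all covariates are picked by significance tests and that nearly all the precision of adjustment is given up. Aim 1 rules this out for the LSAS, SPIN, PHQ-9, BSI-18, job search behaviour and job-search self-efficacy, all of which Table 4 schedules at baseline. Step 4 shows a loss of about 2 to 5 power points for these outcomes, depending on how far the extra covariate overlaps the baseline score.

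A reader might also infer that the rule inflates Type I error. The simulations show the opposite: .041 to .048 under automatic entry. They do not cover free choice by the analyst, which the wording allows and which cannot be simulated without a rule.

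Three further replies have some force:

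- **Considering is not entering.** True. The power figures describe automatic entry at .05, which is only one reading. The softer wording leaves the model less determined, so it does not cure the problem.
- **Testing balance can show that allocation failed.** This is a legitimate integrity check and may stay. The objection is to using its result to choose covariates.
- **The pilot effect on hours was larger than .34.** At the pilot value of .46, non-centrality is .46/.1183 = 3.89 and power is already .97 unadjusted, so adjustment could add little. The loss matters if the true effect is nearer the .34 on which the plan bases its power.

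**Conclusion.** The point holds for the additional covariates, and mainly for paid work hours. For that outcome the baseline score has almost no spread, so the significance rule is the only stated route to useful adjustment in the main model. At d = .34 the rule leaves power at about .81 to .82, where a prespecified covariate would give .86 to .94. For outcomes with an informative baseline score the loss is small.

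The sample size is not in question: the stated .80 reproduces without any covariate.

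The sizes rest on assumed correlations of .4 to .6, one covariate, automatic entry at .05, and an analysis of group means at one time point in place of the planned three-level model. Work hours will probably include many zeros, so the figures for that outcome are indicative. The case for fixing the set in advance does not depend on them. This is a moderate point that should be corrected because the change is nearly free.

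**What to change.** Delete the sentence that draws covariates from significant baseline differences. In its place, state one covariate set for each outcome, fixed before unblinding and applied whatever the observed balance:

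- the baseline score of the outcome, where one exists and varies;
- site;
- a short list of named prognostic variables already collected. For work hours, education and prior work experience are candidates; Aim 3 already names both as potential moderators.

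Report baseline balance descriptively, with means and standardised differences by arm. If a test of the allocation process is wanted, keep it as an integrity check with no bearing on the model. Label any model with further covariates as a sensitivity analysis.

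The cost is SAP wording, with no new data or staff. The team gives up post hoc choice of covariates and spends a few degrees of freedom. With 50 groups this argues for a short list, particularly for group-level terms such as site.

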WCBT retention. All JVS consumers will receive a schedule of available services along with suggested activities recommended by their assigned caseworkers that includes a schedule of WCBT sessions. If a participant misses a session, s/he will be contacted by the group leader to ascertain reasons for failing to attend, and to discuss barriers and potential attendance remedies. Participant addresses and phone numbers will be updated through regular contact from the time of baseline, throughout active treatment, and follow-up. Participation will be encouraged by a \$40 payment for each assessment. In the R34 trial, participant dropout rate from WCBT was very low at 6%; therefore, we estimate a maximum 15% rate of drop-out from WCBT.

Assessment retention. Maintenance of samples for assessment purposes was strong in our R34 project (91% of the ITT sample). However, we are improving our retention practices in keeping with published guidelines for retaining at-risk study populations published by [name] and colleagues (90). These strategies include collecting contact information from all contact persons not living with the participant who know of their whereabouts, providing business cards with contact information for next appointment time and payment amount, initiating contact efforts well before assessment time, persisting with contact attempts throughout the follow-up period regardless of prior assessment session attendance, JVS employees reminding participants of

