Measures of subjects' social anxiety symptoms. The primary symptom measure for assessing treatment outcome will be the Liebowitz Social Anxiety Scale (LSAS: Liebowitz, 1987). It assesses fear and avoidance of several social interaction and performance situations. The LSAS total score has excellent internal consistency and has demonstrated sensitivity to change following pharmacological and cognitive-behavioral therapy (Heimberg et al., 1998; 1999). The Social Phobia Inventory (SPIN) will assess social anxiety symptoms across assessment time points, while the Mini-SPIN (Connor et al., 2001) will assess change in social anxiety symptoms among participants randomized to the treatment condition, weekly throughout active treatment.

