participants, family members, or worsening scores on the Beck Scale for Suicidal Ideation (BSS), which will be given weekly. A safety-monitoring plan will be in place for participants experiencing worsening severity during the waiting period prior to treatment assignment or during the follow-up period. Although we anticipate that the time from point of study enrollment up to commencement of treatment will be short (approximately 3 weeks), participants will be contacted weekly by a member of the research team to clinically reassess SocAD symptom severity and other clinical signs that may indicate need for removal from the study during the waiting period. During the follow-up period, clinical reassessments for worsening severity will occur on a monthly basis via the telephone. In addition, at first contact, participants will be provided with an information sheet detailing procedures for contacting investigators should their social anxiety symptoms, comorbid symptoms, or risk for harm to self or others become a source of concern. If any of these scheduled reassessments reveal worsening social anxiety symptoms, comorbid symptoms, or risk for harm to self or others, a repeat face-to-face assessment will be completed, including the LSAS, PHQ-9, BSS, and measures of functioning. If there is a clinically significant worsening on the LSAS, PHQ-9, or BSS relative to the prior assessment, significant effort will be made to expedite entry into the best available treatment outside the research protocol.

Treatment Non-Participation. Given our intent to gather participant consent prior to enrollment and our previous experience with WCBT for SocAD, we expect complete participant non-participation to be limited. If a participant does not participate in a session they will be counseled by one of the group leaders and a plan will be put in place to encourage participation. However, should any participant completely fail to participate for three consecutive sessions with associated group leader counseling, they will be dropped from WCBT and offered continued services at JVS. All efforts will be undertaken by the group leader to encourage the participant to participate in the treatment before initiating withdrawal from the trial.

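### Whether departures from missing-at-random are examined should not depend on an ignorable verdict from pattern mixture modelling; report one pre-specified MNAR analysis in any case

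*Combined protocol and SAP*

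**What the plan says.** The paragraph on the general approach to quantitative analysis, at the end of the section on power and statistical strategy, sets out three steps.

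1. As in the pilot, pattern mixture modelling is used "to determine whether missing assessments at various time points affect study conclusions or are" ignorable, which the plan equates with conditionally missing at random.
2. "Missing data determined to be ignorable will be estimated using expectation maximization and multiple imputation procedures" suited to longitudinal data.
3. "Sensitivity analysis will be used to examine the possible impact on study conclusions involving any missing data found to be nonignorable".

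It gives no identifying restriction for the pattern mixture model, no criterion for the classification, and no method or range for the sensitivity analysis. No other section plans an MNAR analysis that is always reported.

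On the likely amount of missing data, the same paragraph says "In our pilot, our post-intervention retention rate was 86%; retention was equal across arms", and adds that pilot missing-data patterns were unrelated to outcomes. The section on assessment retention says "Maintenance of samples for assessment purposes was strong in our R34 project (91% of the ITT sample"). Neither section projects retention at 52 weeks for this trial. The 15% ceiling given under WCBT retention is dropout from treatment, not missed assessments.

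**The concern.** Whether data are MAR or MNAR, given what was observed, cannot be settled from the observed data. A pattern mixture model can show that dropout pattern is related to observed outcomes. It identifies the unobserved part of each pattern only through assumptions that the analyst supplies. A null finding is therefore compatible both with MAR and with substantial departures from it.

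The plan nevertheless lets that finding choose the branch. The pilot check came out null and the trial will follow the pilot's approach, so the sensitivity branch could well go unused. 

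The point bears most on the LSAS: "The primary symptom measure for assessing treatment outcome will be the Liebowitz Social Anxiety Scale", and Table 4 schedules it only at baseline, post-treatment and the three follow-ups. Paid hours are better covered, by weekly timecards, a check of missing patterns for each method, and employment verification by JVS staff. At stake is whether readers can see how different the missing participants would have to be before a conclusion changes.

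**Working it through.** **1. Can observed data reveal the departure?** A simulation with 400,000 cases, a baseline covariate, an outcome with SD 1 and about 86% observed. Unobserved outcomes were shifted by a fixed amount.

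| Shift in unobserved outcomes | Observed slope / intercept | Observed mean | MAR estimate | True mean |
|---|---|---|---|---|
| 0 | .602 / .000 | .024 | −.002 | −.001 |
| −0.5 SD | .602 / .000 | .024 | −.002 | −.073 |
| −1 SD | .602 / .000 | .024 | −.002 | −.145 |

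Everything observable is identical in the three rows; only the truth moves.

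**2. Set-up for the size of the risk.** From the Aim 1 power paragraph: 300 people, 50 groups of 6 (so 150 per arm), two-sided .05, ICC .01 or .03, detectable d = .34, pilot effects from .46 (hours worked) to 1.36 (social avoidance). Retention r: .91 and .86 from the documents; .80 is an assumption.

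SE = √[(2/(150r)) × (1 + (6r − 1) × ICC)], critical t on 48 df = 2.011.

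*Reproducing the plan:* at r = 1 and ICC .01, SE = √(.01333 × 1.05) = .1183. A noncentral t on 48 df gives detectable effects of .300, .338 and .391 at power .7, .8 and .9 (plan: .30, .34, .39). At ICC .03 and power .8 it gives .354 (plan: .36). The set-up matches the plan closely.

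**3. Tipping point.** Shift only the missing WCBT outcomes and leave missing VAU outcomes at MAR. The effect falls by (1 − r) × delta, so the tipping delta = (d − 2.011 × SE)/(1 − r). If missing WCBT participants lose the whole benefit, delta = d, the estimate is d × r, and t = d × r/SE.

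Worked line, r = .86 (21 missing per arm), ICC .01: SE = √[(2/129) × 1.0416] = .1271; threshold 2.011 × .1271 = .256; tipping delta = (.34 − .256)/.14 = 0.60 SD. Whole-benefit loss: .34 × .86 = .292; t = .292/.1271 = 2.30; p = .026.

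| d = .34 | r = .91 | r = .86 | r = .80 (assumed) |
|---|---|---|---|
| ICC .01: SE | .1237 | .1271 | .1315 |
| ICC .01: tipping delta (SD) | 1.01 | 0.60 | 0.38 |
| ICC .01: p, whole benefit lost | .016 | .026 | .044 |
| ICC .03: tipping delta (SD) | 0.90 | 0.53 | 0.33 |
| ICC .03: p, whole benefit lost | .020 | .032 | .052 |

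**4. Larger effects (ICC .01).** At d = .46 the tipping deltas are 2.35, 1.46 and 0.98 SD at r = .91, .86 and .80. At d = 1.36 they are 7.89 SD at r = .86 and 5.48 SD at r = .80.

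**5. Baseline adjustment.** The plan states that "Individual baseline scores on each outcome variable will be incorporated as level 2 covariates to increase the precision and statistical power". Assuming a baseline correlation of .5 (not in the documents), SE is multiplied by √.75. For d = .34 and ICC .01 the tipping deltas become 1.38, 0.85 and 0.55 SD. At r = .80 the whole-benefit-loss p is .021 (ICC .01) or .026 (ICC .03).

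**6. Break-even retention.** Solving .34 × r = 2.011 × SE(r): whole-benefit loss removes significance below about 78% retention at ICC .01 (.785) or 80% at ICC .03 (.804). With the assumed correlation of .5 these become 71% and 73%.

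**The case against.** A reader might infer that an ignorable verdict leaves the MAR results with no examination of departures at all. The text does not support that. Pattern mixture modelling is a recognised framework for nonignorable missingness, it is planned without condition, and its stated purpose includes whether missing assessments affect conclusions. It is itself a form of sensitivity analysis. What stands is narrower: without stated identifying restrictions its result depends on unnamed assumptions, and a null result does not prove ignorability.

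The plan also never says that sensitivity analysis is confined to nonignorable data, or that pattern mixture results will go unreported. That is fair. Still, imputation is assigned to one class and sensitivity analysis to the other, and this split is the plain reading.

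A reader might also infer that the trial's result is fragile. The figures do not show this. At both documented retentions a result at the detectable effect survives loss of the whole benefit. The fragile case combines the smallest detectable effect, a retention found in neither document section, a shift in one arm only, and an unadjusted single-time-point analysis that the trial does not plan. The documents give no pilot effect for the LSAS total, but anywhere in the pilot range the margin is much larger.

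Finally, existing data make MAR more plausible. The Mini-SPIN is collected in both arms during the active phase (the section on VAU active phase questionnaires, with Table 4), which helps with early dropout though less at 26 and 52 weeks. "During the follow-up period, clinical reassessments for worsening severity will occur on a monthly basis via the telephone", and missed 52-week interviews may be done by telephone. These reduce the problem; none of them alone tests departures from MAR.

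**Conclusion.** The point holds as a cheap improvement to the plan, not as a demonstrated threat to its conclusions. The plan makes a classification that observed data cannot support decide whether a dedicated sensitivity analysis is done.

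The likely size is modest: at d = .34 without baseline adjustment, p stays between .016 and .032 under whole-benefit loss across the documented 86% to 91% retention and both ICCs. It reaches .052 only at an assumed 80% retention with ICC .03.

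These figures rest on one time point and a shift in WCBT only. Repeated measures and baseline covariates should widen the margin. Because the 86% is a post-intervention figure and no 52-week retention is projected, which case will apply cannot be known in advance.

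**What to change.** Drop the ignorable/nonignorable gate. Keep the MAR analysis as primary, with data already collected as auxiliary variables in the imputation: active-phase Mini-SPIN in both arms, weekly timecards, and the monthly telephone reassessments where recorded.

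Whatever the pattern mixture result, report one pre-specified MNAR sensitivity analysis for LSAS and paid hours at 12, 26 and 52 weeks, with its assumptions fixed before outcomes are compared by arm. Either form would serve:

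- delta-adjusted or tipping-point multiple imputation, varied by arm and respecting the groups; or
- the pattern mixture model already planned, with stated identifying restrictions and a delta range.

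The cost is a few sentences in the analysis plan and a little more analysis work. Data collection does not change.
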